## List of Abbreviations AND ACRONYMS

AAFQ	Arizona Activity Frequency Questionnaire
AE	Adverse event
AS	Active Surveillance
BMI	Body mass index
BUN	blood urea nitrogen
CI	Confidence Interval
CRF	case report form
DPP	Diabetes Prevention Program
DM	Diabetes Mellitus
DMC	Data Monitoring Committee
DSMB	Data Safety Monitoring Board
DXA	Dual x-ray absorptiometry
EDC	Electronic data capture
EPIC	Expanded Prostate Cancer Index
FDA	Food and Drug Administration
FHCRC	Fred Hutchinson Cancer Research Center
GCP	Good Clinical Practice
GXT	Graded Exercise Treadmill test
HbA1C	Hemoglobin A1C
HIPAA	Health Insurance Portability and Accountability Act of 1996
HR	Hazard Ratio
HRQOL	Health Related Quality of Life
ICF	informed consent form
ICH	International Conference on Harmonisation
IGF-BP3	Insulin like Growth Factor Binding Protein 3
IGF-1	Insulin like Growth Factor 1
IGF-1R	Insulin like Growth Factor 1 Receptor
IR	Insulin Receptor
IRB	Institutional Review Board
MAX-PC	Memorial Anxiety Scale for Prostate Cancer
NIH	National Institute of Health
PCPT	Prostate Cancer Prevention Trial
PE/DVT	Pulmonary embolism/deep venous thrombosis
PI	Principal Investigator
PCa	Prostate Cancer
PCSM	Prostate Cancer Specific Mortality
PSA	Prostate Specific Antigen
QOL	Quality of Life
RP	Radical Prostatectomy
RC	Research Coordinator
SAE	serious adverse event

## PROTOCOL SYNOPSIS

TITLE	PALS: Prostate Cancer Active Lifestyle Study
SPONSOR	R01 CA184075-01A1
FUNDING ORGANIZATION	National Cancer Institute
NUMBER OF SITES	Fred Hutchinson Cancer Research Center
RATIONALE	
Prostate cancer (PCa) is the most common cancer diagnosis in men today and the second leading cause of cancer-related mortality in men, accounting for almost 30,000 deaths annually. Obesity contributes to PCa-specific mortality (PCSM), increasing risk by 20-160%, but the causal mechanisms remain unknown. Men on Active Surveillance (AS), where low risk PCa patients are monitored with regular PSA blood tests, physical exams and prostate biopsies, provide an ideal population to study the effects of obesity on adverse outcomes in relation to a lifestyle intervention: (1) these men are cancer survivors not having had aggressive treatment, and may be more able and motivated to undergo a lifestyle intervention; and (2) they have intact tumors which allow for ongoing tumor tissue based analyses to be conducted. Despite their initial lower risk status, 50% of these patients will experience disease progression requiring active treatment. We hypothesize that obesity enhances tumor growth, leading to conversion of low-risk to high-risk disease. Thus, implementing a lifestyle intervention against obesity and understanding the biologic mechanisms linking obesity and PCa outcomes could have a profound effect on clinical practice through reducing overtreatment and its adverse side effects, reducing health care costs, and reducing patient anxiety. Identifying factors that may slow or prevent tumor progression in AS patients will have substantial clinical and public health impact by improving patient outcomes and reducing health cancer expenditures.

STUDY DESIGN	
This is a randomized controlled trial to investigate the effects of a 6-month lifestyle intervention based on the Diabetes Prevention Program (DPP) on glucose regulation biomarkers, health related quality of life and pathologic features of follow-up biopsies in overweight and obese men with prostate cancer on Active Surveillance

PRIMARY OBJECTIVE	
The study has the following primary specific aims:
 
 
1. To test whether the DPP lifestyle intervention (vs. control) improves serum fasting glucose;
 
2. To test whether the DPP lifestyle intervention (vs. control) improves serum biomarkers of glucose regulation (insulin, C-peptide, insulin-like growth factor-1 (IGF-1), IGF binding protein 3 (IGF-BP3) and adiponectin);
 
3. To test whether the DPP lifestyle intervention decreases the levels of insulin receptor or insulin-like growth factor-1 receptor (IGF-1R) in PCa tissue epithelium on follow-up prostate biopsy;
 
4. To test whether PCa patients randomized to the DPP lifestyle intervention sustain the lifestyle changes for at least 6 months after the end of the intervention period.
 

SECONDARY OBJECTIVES	
The secondary objectives are to:
 
 
1. To evaluate whether the DPP lifestyle intervention improves health-related quality of life;
 
2. To evaluate whether the DPP lifestyle intervention effects on pathologic features of follow-up prostate biopsies.
 

NUMBER OF SUBJECTS	200
SUBJECT SELECTION CRITERIA: Inclusion Criteria	
Inclusion Criteria:
 
 
1. histologically confirmed adenocarcinoma of the prostate, clinically localized, low or low-intermediate risk disease (T1C/T2a, Gleason≤7 (3+4), PSA < 20);
 
2. Primary treatment is AS with planned annual surveillance biopsies;
 
3. BMI≥25 kg/m2; and
 
4. Able to make the required dietary changes
 
5. Physically able to undertake an exercise program.
 

SUBJECT SELECTION CRITERIA: Exclusion Criteria	
Exclusion Criteria:
 
 
1. Current, recent (<1 year), or planning to join a weight loss program, undergo weight loss surgery, or take appetite suppressants;
 
2. Steroid hormone (ADT) use within past 12 months;
 
3. Significant cardiovascular disease precluding an exercise program, including recent (within 6 months) myocardial infarction or stroke, pulmonary edema, myocarditis, pericarditis, unstable angina, PE/DVT, uncontrolled hypertension (SBP>200; DBP>110), uncontrolled arrhythmia, heart failure; or
 
4. Insulin dependent DM and/or metformin use.
 
5. MD confirmed cognitive impairment
 
6. Current alcohol or narcotic abuse
 

DURATION OF SUBJECT PARTICIPATION AND DURATION OF STUDY	
Subjects will be on study for up to 1 year
 
Treatment: 6 months
 
Follow-up: 6 months
 
The total duration of the study is expected to be 4 years

PRIMARY ENPOINTS	
Primary Aims 1 and 2: Compare change in fasting glucose, C-peptide, insulin, IGF-1, IGF-BP3, and adiponectin levels relative to baseline between the intervention and control arms.
 
Primary Aim 3: We will test whether the change in expression of IR, IGF-1R, and AKT on prostate cancer epithelial cells from follow-up surveillance biopsy (6 months post-randomization) relative to 'baseline' (biopsy ~6 months prior to randomization).
 
Primary Aim 4: We will test whether PCa patients randomized to the intervention arm are able to sustain the beneficial changes in weight and glucose regulation an additional 6 months after the active intervention.

SECONDARY ENDPOINTS	
Secondary Aim 1. We will test whether the change in HRQOL, namely urinary and sexual QOL and bother, relative to baseline, differs between the intervention and control arms
 
Secondary Aim 2. We will use a two-sample test of proportions to determine whether the proportion of participants with adverse pathology (Gleason upgrading, increase in number of positive cores, cores>50% positive) on follow-up surveillance biopsy differs between intervention and control arms.

STATISTICS Primary Analysis Plan	
Aims 1 and 2: Global assessment of intervention effects will be evaluated using a two-sided t-test or Wilcoxon rank sum test if normality of the measurement is questionable (as determined by QQ-normal plots). Further analysis will quantify effects of patient age, BMI and other body composition measures on change in fasting glucose using linear regression. Differential effects between intervention and control arms will be quantified using interaction terms. All analyses will compare effects based on intention-to-treat.
 
Aim 3: Global assessment of intervention effects will be evaluated using a two-sided t-test (or Wilcoxon rank sum test). Linear regression will be used to assess associations of IR, IGF-1R, and AKT expression with systemic measures of glycemic control at 6 months.
 
Aim 4: We will follow the DPP research group characterization of sustained weight loss as maintenance of a 7% reduction in weight and sustained glucose regulation as maintenance within 5% of 6-month levels. Because not all participants will achieve 7% weight loss at 6 months, we will look in the subset of participants who did and did not achieve this goal both separately and combined. A one-sample test of proportions will be used to determine whether the proportion of participants that are able to sustain lifestyle changes differs from zero.

Rationale for Number of Subjects	Our power calculations give the minimally detectable intervention effects for endpoints in Primary Specific Aims, setting two-sided alpha error at 5% and power at 80%. We have set a sample size of 100 in each of the intervention and control arms, based both on our overall evaluation of minimum detectable differences across the range of study endpoints and on a reasonable estimate of the number of men we can recruit. The sample size allows for a drop-out rate of 5%, and power calculations assume correlations of 0.70 between baseline and follow-up measures.

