#### Human studies. Small

studies have evaluated serum biomarkers of glucose regulation and PCa aggressiveness and cancer outcomes. In studies of men with diabetes undergoing RP, higher pre-RP HbA1C levels were associated with a

Table 2: Animal studies of diet and resultant PCa tissue receptor changes

Author, year	Diet	Receptor levels in diet arm
Narita, 2008 	Low fat	$\downarrow$ IGF-1R
Powlony, 2008 	Caloric Restriction	$\downarrow$ IGF-1R
Venkateswaran, 2007 	Low fat, low carb	$\downarrow$ IR and $\downarrow$ phos-Akt
Kobayashi, 2008 	Low fat	$\downarrow$ phos-Akt
Mavropoulus, 2009 	No carb	$\downarrow$ phos-Akt

greater risk of extracapsular disease and aggressive PCa. In an analysis of the control arm of the Prostate Cancer Prevention Trial (PCPT) by one of our investigators (MN), higher C-peptide (an insulin surrogate) levels were associated with an 88% increased risk of aggressive PCa. In addition, longitudinal studies of men treated for PCa have found direct associations between markers of glucose regulation and PCSM. In one study, a higher mean fasting insulin level at diagnosis was found in those who died of PCa. In the Physicians Health Study, PCa cases with the highest C-peptide concentrations ( $>2.7$ ) had more than a 2-fold increased risk of PCSM (HR 2.4, 95% CI 1.3-4.3) vs. those with the lowest concentrations ( $<1.0$ ).

In previous studies, we determined that elevated glucose levels at PCa diagnosis independently predicted risk of recurrence. Men with PCa undergoing local therapy who had glucose  $\geq 100$  mg/dL at diagnosis had a 50% increased risk of recurrence (HR 1.5, 95% CI 1.1-2.0) vs. those with glucose level  $<100$  mg/dL. These findings are in line with results from studies in several other cancers, including breast, colon, liver and brain

cancers, which have also found that higher glucose levels are associated with a greater risk of tumor progression. In summary, markers of glucose regulation may foreshadow PCa progression and glucose control may be a modifiable risk factor for PCa recurrence.

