#### **1.4 Diabetes Prevention Program**

The DPP studied over 3,000 participants with elevated fasting glucose levels randomized to metformin, a 6-month lifestyle modification program or placebo. The goal of the lifestyle modification program was a 7% reduction in body weight through a structured dietary program and at least 150 minutes of weekly physical activity. The lifestyle intervention decreased incident diabetes mellitus (DM) by 58% vs. controls, while metformin reduced incident DM by 31%. Fasting glucose declined from a mean of 107 to 101 mg/dl in the lifestyle group whereas no change was seen in the placebo group. Long term follow-up of the DPP has demonstrated sustained weight loss at 10 years, which is an important consideration as other studies of dietary interventions in men with PCa have used diets that are difficult to maintain over the long-term (e.g., vegan, low glycemic and prepared meals). The results of the lifestyle intervention have also been found to be cost-effective and cost saving. A meta-analysis of weight loss studies based on the DPP lifestyle modification program consistently shows statistically significant and clinically relevant reductions in weight; however, the majority of participants in those studies were women and no studies to date have been conducted in older men with cancer. Despite this, there are indications that older men may be an ideal population for the DPP lifestyle intervention. Older participants ( $\geq 60$  years) compared to younger groups (25-44 yrs. and 45-59 yrs.), had the greatest weight loss (mean -6.4 kg vs. -4.1 and -5.0 kg respectively,  $p < 0.001$ ) and more commonly met the exercise goal (48% vs. 34% and 38% respectively,  $p < 0.001$ ). The lifestyle intervention was more effective than metformin at weight loss with increasing age ( $p = 0.005$ ). In addition, compared to women, men lost more weight ( $p < 0.01$ ) and performed higher levels of physical activity ( $p < 0.05$ ) in the lifestyle intervention. However, since only 20% of participants were older than 60 years of age, fewer than 1/3 of participants were men, and none of the participants had cancer, whether these results will have similar effects in a PCa population are unknown, but certainly these data provide evidence that the DPP intervention can succeed in this population. Thus, the DPP intervention offers a novel strategy to improve PCa patient outcomes and yield insights on biological pathways by which obesity may delay or prevent disease progression.

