### **6.3 Exclusion Criteria**

1. current, recent (<1 year), or planning to join a weight loss program or take appetite suppressants;
2. Steroid hormone use (ADT) within the past 12 months;
3. significant cardiovascular disease precluding an exercise program, including recent (within 6 months) myocardial infarction or stroke, pulmonary edema, myocarditis, pericarditis, unstable angina, PE/DVT, uncontrolled hypertension (SBP>200; DBP>110), uncontrolled arrhythmia, heart failure; or
4. 4) insulin dependent DM and/or metformin use.
5. MD confirmed cognitive impairment
6. Current alcohol or narcotic abuse

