## 7.3 Randomization

Participants will be randomly assigned to either the intervention or control arm using a computerized program. In order to evenly distribute men to treatment arm, randomization will be blocked on BMI (25-29.9 or 30+) and age (<65years or 65+).

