## **11 STATISTICAL METHODS AND CONSIDERATIONS**

**Primary Aim 1.** The primary analysis will compare change in fasting glucose level relative to baseline between the intervention and control arms. Global assessment of intervention effects will be evaluated using a two-sided t-test or Wilcoxon rank sum test if normality of the measurement is questionable (as determined by QQ-normal plots). Further analysis will quantify effects of patient age, BMI and other body composition measures on change in fasting glucose using linear regression. Differential effects between intervention and control arms will be quantified using interaction terms. All analyses will compare effects based on intention-to-treat.

**Primary Aim 2.** Additional analyses will compare changes in levels of C-peptide, insulin, IGF-1, IGF-BP3, and adiponectin relative to baseline measurements between the intervention and control arms. As in Aim 1, we will compare global and subgroup effects based on intention-to-treat analyses.

**Primary Aim 3.** We will test whether the change in expression of IR, IGF-1R, and AKT on prostate cancer epithelial cells from follow-up surveillance biopsy (6 months post-randomization) relative to 'baseline' (biopsy ~6 months prior to randomization, see Fig. 3) differs between intervention and control arms. Global assessment of intervention effects will be evaluated using a two-sided t-test (or Wilcoxon rank sum test). Linear regression will be used to assess associations of IR, IGF-1R, and AKT expression with systemic measures of glycemic control at 6 months. Exploratory analyses will also evaluate associations between adverse pathology, biomarkers of glycemic control and IR/IGF-1R/AKT expression.

**Primary Aim 4.** We will test whether PCa patients randomized to the intervention arm are able to sustain the beneficial changes in weight and glucose regulation an additional 6 months after the active intervention. We will follow the DPP research group characterization of sustained weight loss as maintenance of a 7% reduction in weight and sustained glucose regulation as maintenance within 5% of 6-month levels. Because not all participants will achieve 7% weight loss at 6 months, we will look in the subset of participants who did and did not achieve this goal both separately and combined. A one-sample test of proportions will be used to determine whether the proportion of participants that are able to sustain lifestyle changes differs from zero.

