### 11.1 Sample Size and Randomization

Our power calculations give the minimally detectable intervention effects for endpoints in Primary Specific Aims, setting two-sided alpha error at 5% and power at 80%. We have set a sample size of 100 in each of the intervention and control arms, based both on our overall evaluation of minimum detectable differences across the range of study endpoints and on a reasonable estimate of the number of men we can recruit. The sample size allows for a drop-out rate of 5%, and power calculations assume correlations of 0.70 between baseline and follow-up measures.

Table 4 gives the minimally detectable differences between treatment arms for serum and tissue biomarkers of glucose regulation. We have used a variety of data sources to complete these tables, attempting whenever possible to use data generated from human studies. For serum biomarkers of glucose regulation, we use data from our own pilot study and the PCPT, and for tissue expression of IR/IGF-R1 and AKT we use data from Cox et al. The minimum detectable intervention effects range from 5.3% for serum glucose to 33.1% for insulin. Previous studies have shown that dietary change can induce the following intervention effects: 7% for fasting glucose, 40% for insulin and 2.2 % for adiponectin. Our pilot study based on the DPP demonstrated an intervention effect of ↑9.7% for IGFBP3, ↓38% for insulin and ↓14% for C-peptide. Based on these observations, we will have good power to detect changes in all serum biomarkers of glucose regulation, consistent with those seen in other human intervention studies.

For expression of IR, IGF-1R and AKT on surveillance prostate biopsies, the minimum detectable intervention effects are 29.2%, 46.3% and 26.5%, respectively. Previous experimental studies in animals have

**Table 4. Minimal detectable differences in serum and tissue biomarkers at 80% power,  $\alpha=0.05$  given a sample size of 200 (100 in each of the lifestyle intervention and control arms)**

Biomarker	Baseline Mean (SD) or n (%)	Minimum Detectable Difference (MDD)	
		Mean	% of mean
Primary Aim 1 - Serum			
Fasting glucose, mg/dL	106.3 (12.6)	5.6	5.3%
Primary Aim 2 - Serum			
C-peptide, ng/mL	1.7 (1.2)	0.54	31.6%
Insulin, pmol/L	138.0 (102.0)	45.7	33.1%
IGF-1, ng/mL	232.7 (75.4)	33.8	14.5%
IGF-BP3, ng/mL	4317.6 (975.2)	436.5	10.1%
Adiponectin, ug/mL	6.1(3.9)	1.8	29.0%
Primary Aim 3 – Tissue			

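### The Aim 1 regression tests age, BMI and body composition for differential effects but omits baseline fasting glucose, so a glucose-dependent benefit would be diluted with no pre-specified analysis to show it

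*Combined protocol and SAP*

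**What the plan says.** The Synopsis (Primary Analysis Plan, Aims 1 and 2) and Section 11 (Primary Aim 1) describe the same two steps. First, change in fasting glucose is compared between arms by a two-sided t-test, or a Wilcoxon test if normality is doubtful. Then: "Further analysis will quantify effects of patient age, BMI and other body composition measures on change in fasting glucose using linear regression". Section 11 continues: "Differential effects between intervention and control arms will be quantified using interaction terms". For Aim 2 it adds "As in Aim 1, we will compare global and subgroup effects based on intention-to-treat analyses", which refers back to Aim 1 and names no further subgroup.

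Baseline fasting glucose enters only through the change score. It is not named as a covariate, effect modifier or subgroup, and it is not a randomization factor (Section 7.3 uses BMI and age). Section 7.5 collects twelve-hour fasting blood at baseline, so the value will be available.

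Section 6.2 admits men by tumour risk, active surveillance, BMI of at least 25 and ability to follow the programme. The only rule in Section 6.3 related to glycaemia excludes "insulin dependent DM and/or metformin use". Neither section sets a fasting-glucose threshold. Section 1.4 describes the source of the intervention: "The DPP studied over 3,000 participants with elevated fasting glucose levels". There, mean fasting glucose fell from 107 to 101 mg/dL with the lifestyle programme and did not change on placebo.

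**The concern.** The plan already intends to look for differential effects, so the question is which modifiers it names. A man's starting glucose is an obvious candidate when the outcome is change in glucose. The cited DPP result comes from people selected for elevated glucose, and this trial does not select on it. Men with normal fasting glucose may have less to gain.

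If so, the overall comparison mixes two effects. A modest average could be a DPP-sized benefit in men with raised glucose combined with little in the rest. A clearly positive average could be extended to men with normal glucose who gained nothing. BMI is only a partial proxy for glucose, so the planned BMI interaction would not settle the matter. A glucose split chosen after seeing the data would carry much less weight than one written down now.

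**Working it through.** **Inputs.** From Section 11.1 and Table 4: baseline mean 106.3 and SD 12.6 mg/dL, two-sided alpha 5%, 100 per arm less 5% drop-out = 95, correlation r = 0.70, minimum detectable difference (MDD) 5.6 mg/dL. From Section 1.4: DPP effect 107 − 101 = 6 mg/dL. From Section 1.3: the 100 mg/dL cut-off used in the investigators' recurrence study. My assumptions: normally distributed baseline glucose; a 6 mg/dL effect at or above 100; all, half or none of it below 100; r = 0.5 as a sensitivity value that is not in the documents.

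**The plan's own figure.** With r = 0.70, the SD of change is 12.6 × √(2 × 0.30) = 9.76. The MDD is 2.80 × 9.76 × √(2/95) = 3.97 mg/dL, not 5.6. Reaching 5.6 at 95 per arm needs r of about 0.40. That mismatch is a separate matter, but it is a reason to show a lower correlation alongside 0.70.

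**Share and average effect.** The share below 100 is Φ((100 − 106.3)/12.6) = Φ(−0.5) = 0.309, so 0.691 are at or above it: about 66 and 29 of 95 per arm. Average effect = 6 × (0.691 + 0.309k), which gives 6.0, 5.07 and 4.15 mg/dL for k = 1, 0.5 and 0.

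**Power of the planned t-test on change, k = 0, r = 0.70.**
- Control-arm variance: 9.76² = 95.3.
- Intervention-arm variance is larger because the effect depends on baseline: 95.3 + 36 × 0.691 × 0.309 + 2 × 6 × 0.30 × (12.6 × 0.352) = 95.3 + 7.7 + 16.0 = 118.9 (rounded).
- SE = √((95.3 + 118.9)/95) = 1.50.
- Power = Φ(4.15/1.50 − 1.96) ≈ 79%. Ignoring the extra variance gives 83%.

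The same steps at r = 0.5 give variances of 158.8 and 193.1, SE 1.92 and power of about 58%. Using the SE implied by the printed MDD (5.6/2.80 = 2.0) gives about 55%.

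| Effect below 100 mg/dL | Average effect | Power, r = 0.70 | Power, r = 0.5 |
|---|---|---|---|
| 6 (same) | 6.0 | 99% | 91% |
| 3 (half) | 5.07 | 94% | 76–77% |
| 0 (none) | 4.15 | 79% | 58% |

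Simulation at 95 per arm agrees within about two percentage points.

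**If fewer men have raised glucose than Table 4 implies.** With none of the effect below 100 and change SD 9.76, a 50% share gives an average of 3.0 mg/dL and 56% power. A 30% share gives 1.8 mg/dL and 25%. These two ignore the extra variance, so they are slightly optimistic.

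**What the added terms deliver, k = 0.**
- Baseline-adjusted overall difference: power about 87% (r = 0.70) or 73% (r = 0.5).
- Baseline-adjusted difference in men at or above 100: about 97% or 87–88%.
- Dichotomous interaction: residual SD = 12.6 × √(1 − r²) = 9.0 or 10.9; SE = SD × √(2/66 + 2/29) = 2.84 or 3.44; power for a 6 versus 0 contrast about 56% or 41%.
- Continuous interaction, by simulation: power about 35–37% (r = 0.70) or 27% (r = 0.5), within a few points of simulation error. Stratum effects read off the linear term come out at about 5.2–5.3 and 1.7 mg/dL where the truth is 6 and 0.
- Approximate 95% CI half-widths for stratum differences at r = 0.70: 1.96 × 9.0 × √(2/66) = 3.1 mg/dL at or above 100, and 1.96 × 9.0 × √(2/29) = 4.6 mg/dL below 100.

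**The case against.** A reader might infer that the effect would be averaged away. The figures do not support that. At the correlation the plan states, the t-test has about 79% power even with no benefit at all below 100, and 94% with half the benefit. The 58% figure needs a correlation that the documents do not give. Dilution is the right word.

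A reader might also infer that the protocol's own evidence establishes glucose as an effect modifier. It does not. The recurrence study ("mg/dL at diagnosis had a 50% increased risk of recurrence") is prognostic, and Section 1.4 gives no comparison with people of normal glucose.

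The dilution scenario is itself pessimistic. DPP lifestyle participants started at a mean of 107, close to Table 4's 106.3. Under the normal assumption, men at or above 100 average about 112.7 mg/dL. If benefit rises with baseline, their effect could exceed 6.

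Nor does Section 11.1 tie its benchmark to the DPP. It says "Previous studies have shown that dietary change can induce the following intervention effects: 7% for fasting glucose" and cites other references, so a DPP caveat there would qualify a figure the section does not attribute to that trial.

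Finally, the primary comparison answers Aim 1 as worded, the baseline values remain available for later analysis, and the interaction is weakly powered. All of these objections stand. What they leave untouched is that the plan already fits interactions, leaves this factor out, and could include it at almost no cost.

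**Conclusion.** The point holds in a limited form. Baseline fasting glucose is missing from the factors named for the Aim 1 regression, and no pre-specified analysis would show whether benefit depends on it. If the benefit is confined to men at or above 100 mg/dL, the average falls from 6 to about 4.1 mg/dL and power from 99% to about 79% at r = 0.70. At r = 0.5 it falls from 91% to about 58%. This rests on a normal baseline at Table 4's values and on a differential response that the documents do not demonstrate. The loss is greater if fewer men have raised glucose.

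Two stronger readings should be resisted. The effect in men with raised glucose is not beyond estimation: the data will exist, and only pre-specification is lacking. Enrolment is also not by BMI alone, since tumour risk, surveillance status and the diabetes and metformin exclusions apply too. The primary test is not invalid. I would class this as an optional, cheap improvement.

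**What to change.** In the Synopsis (Primary Analysis Plan, Aims 1 and 2) and Section 11 (Primary Aim 1):

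1. Add baseline fasting glucose as a covariate in the Aim 1 regression.
2. Pre-specify its interaction with arm as a secondary analysis, and report the continuous interaction with its 95% CI.
3. Report baseline-adjusted arm differences with 95% CIs for men below 100 and at or above 100 mg/dL. Take these from an arm-by-stratum term, not from the linear interaction, which distorts them if the true pattern is a step.
4. State that the interaction has limited power (about 27–37% continuous and 41–56% dichotomous for a 6 versus 0 mg/dL contrast), so it is an estimate and not a confirmatory test.
5. Keep the overall intention-to-treat comparison as the primary test.

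Section 11.1 needs no DPP caveat, and eligibility is unaffected. The cost is a few sentences and one more secondary interaction to report and interpret cautiously. No new data, visits or participants are needed, and the covariate also makes the adjusted estimate more precise.
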